9.4 Analysis Methods for secondary and exploratory outcomes

There are three secondary outcomes for the primary aim. The mean change from baseline in UDIstress and UDI-irritative subscores will be compared between groups at 6 months, and the UDI total will be compared at 3 months (see above). The statistical analysis of the three secondary outcomes will be identical to the primary analysis described above for the UDI total score. In addition, the per-protocol analysis will be repeated for the secondary outcomes.

For all continuous exploratory measures, groups will be compared using the same model as the primary analysis described above for the UDI total score.

For any dichotomous outcomes assessed across time, groups will be compared for the odds of the event, and an odds ratio will be estimated from a repeated measures logistic generalized linear regression model with adjustment for baseline value, site and baseline age category, and with treatment, visit and treatment by visit interaction with an unstructured covariance pattern separately within each treatment group for the within-subject repeated measures.

For PGI-I and PGSC, the baseline PGI-S score will be the baseline covariate.

Example code from SAS to produce this analysis is as follows:

```
Proc glimmix;
  class subjectID trtgrp VISIT site;
  model dep_var = bbaseline_var trtgrp site visit trgrp*visit /
      solution link=logit dist=binary oddsratio DDFM=KR;
  random time / type=UN Group=trtgrp subject=subjectID RSIDE;
  lsmeans trtgrp*time / ILINK CL; /*estimates event rates*/
  lsmeans trtgrp*time / oddsratio diff CL; /*estimates ORs*/
  estimate `trt a vs trt b at time 2' trtgrp 1 -1 trtgrp*time 0 1 0 0 0 -10 0 / EXP CL;
Run;
```

Groups will be compared for receipt of additional treatment with chi-squared tests or Fisher's exact test for small event rates.

9.5 Other Analysis Methods

9.5.1 Predictors of Treatment Response

Predictors of response will be identified in a secondary manuscript, and methods for analysis will be documented in a separate SAP prior to beginning of the analysis. Both traditional prediction model as well as machine learning methods will be used. Methods specified in the protocol are as follows:

Regression models will be created to identify predictors of change from baseline to 6 months for UDI total score and stress and irritative subscale scores.

Potential predictors will include age, diary parameters such as number of UUI episodes/3 days, functional bladder capacity, stress and irritative bother severity at baseline, type of urinary incontinence (stress-predominant or urgency-predominant, balanced), and co-existing anterior vaginal wall prolapse.

The relationship between potential predictors and outcomes will be explored in models that include one predictor plus stratification factors (treatment group, site and age group). Predictive models will be constructed using backward selection of predictors. The impact of collinearity between predictors will be assessed and the final model modified as necessary.

We will attempt to create threshold definitions, based on baseline measures of the UDI, IIQ, OAB-q, UDE, and baseline bladder diary parameters in isolation and in combination, that are predictive of clinical success at 6 months. Definitions of success will be based on a change from baseline in total UDI score, UDI-irritative score or UDI-stress score at least as large as the MID for this MUI population (see section 9.5.3).

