2.10 Innovation

This proposal is innovative for several reasons. First, the MUSA study is investigating a population of women who are often excluded from clinical intervention trials but are at high risk for treatment failure. Second, this trial will provide important information regarding baseline predictors of response such as whether urgency-predominance or stress-predominance have different optimal treatments. At the completion of this study, we will better understand whether a surgical treatment that focuses on the urgency component (Botox A) is superior to a surgical treatment that focuses on the stress component (mid-urethral sling) and will obtain predictive information that will be directly applicable to the clinical care of patients with this challenging condition.

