6 SAMPLE SIZE DETERMINATION

MUSA will randomize 146 women to treatment with Botox or Sling in a 1:1 ratio. The sample size was derived to provide sufficient power for the primary Aim (comparison of Botox versus sling after 6 months) assessed for the primary outcome (change in UDI total score).

For the primary outcome (UDI total score change from baseline at 6 months), alpha was set at 0.05 and power was set at 90%.

Sample size estimates were based on an evaluation of minimum important differences (MIDs) and corresponding standard deviation (SD) for the UDI total score from the ESTEEM study of MUI, with support from other published populations of women with urge and stress incontinence; however, the populations on which those MIDs were based might differ from the target population of mixed incontinence for MUSA. Thus, our goal was to power the study to detect a statistically significant difference between groups in change from baseline in UDI total score at 6 months for the UDI MID determined from ESTEEM as that will be a clinically important difference in our population. To use the most accurate standard deviation applicable to MUSA, we calculated the SD based on a mixed effects repeated measures model with adjustment for baseline UDI score and clinical site rather than the SD of the observed data in order to account for improvements in variance estimation from the covariate adjustment planned for MUSA. To most closely match MUSA, this analysis model included all 3-month and 6-month ESTEEM data points after any retreatments and excludes patients with <4 Urge IEs/3 days. The MID for ESTEEM UDI-Total is 26, and the SD=46.5 from the analysis model, resulting in an effect size = 0.56.

Total number of randomized patients required to meet planned power estimates were adjusted for the assumed patient discontinuation rate at 6 months. Based on average estimates from ROSETTA and ESTEEM, we plan for 5% discontinuation rate by 6 months.

The evaluable sample size required at 6 months for 90% power for the primary total UDI outcome is 69 per arm. Because data from ROSETTA and ESTEEM suggests that follow-up at 6 months should be about 95%, a total sample size of 73 randomized per treatment arm is selected (69/0.95 =73), for a total sample size of 146 randomized participants.

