7.8 Multiple Comparisons and Multiplicity

The primary hypothesis will be tested at a nominal two-sided type I error of 0.05. The three secondary outcomes will also be tested at a nominal two-sided type 1 error of 0.05, with no adjustment for multiple comparisons, and thus p-values are descriptive. All p-values for any baseline and demographic characteristics, exploratory outcomes, and safety parameters will also be for descriptive purposes only.

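### The predictor analysis commits to backward selection and a threshold search in about 138 women and names no internal validation; the separate predictor SAP should require it

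*SAP*

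**What the plan says.** SAP 9.5.1 restates the method of Protocol 6.2.3 (repeated for 12 months in the Protocol addendum): models with one predictor at a time plus the stratification factors, and then "Predictive models will be constructed using backward selection of predictors". The outcomes are change in UDI total, stress and irritative scores. The only check named is for collinearity, after which the final model may be altered.

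The SAP adds machine learning, not further specified, and a second exercise: "We will attempt to create threshold definitions, based on baseline measures of the UDI, IIQ, OAB-q, UDE, and baseline bladder diary parameters". These may be used singly or combined, and the aim is to predict success at 6 months. Success means a change at least as large as the MID for this population, which SAP 9.5.3 estimates from MUSA itself.

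Two statements limit what can be concluded. SAP 2 and SAP 9.5.1 place the detailed methods in a separate analysis plan, to be written before that analysis starts. Protocol 6.2.3 and SAP 7.8 class the exploratory aims as descriptive.

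On intended use, Protocol 2.10 says the trial "will obtain predictive information that will be directly applicable to the clinical care of patients with this challenging condition". Protocol 2.9 expects data on which women would do better with which treatment.

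**The concern.** Neither document gives, for this aim, a criterion for staying in the model, a closed candidate list, shrinkage, a hold-out sample, cross-validation or an optimism correction. Bootstrapping is mentioned only for the cost-effectiveness ratio. When predictors and cut-points are chosen and then assessed in the same small sample, the choice exploits chance: R-squared, sensitivity and specificity come out too high, and predictors with no real relation to outcome are retained.

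What is at stake is a secondary manuscript. A reader who takes Protocol 2.10 at its word could apply a reported threshold to the next patient and find that it does not work.

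**Working it through.** **1. Sample size available.** From SAP 6: "MUSA will randomize 146 women to treatment with Botox or Sling in a 1:1 ratio"; "The MID for ESTEEM UDI-Total is 26, and the SD=46.5 from the analysis model, resulting in an effect size = 0.56"; "The evaluable sample size required at 6 months for 90% power for the primary total UDI outcome is 69 per arm". SAP 7.8 makes the test two-sided at 0.05.

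- Normal approximation: n = 2(z0.975 + z0.90)² (SD/δ)² = 2 × (1.960 + 1.282)² × (46.5/26)² = 2 × 10.51 × 3.199 = 67.2, so 68 per arm.
- Noncentral t: 69 per arm, with power 90.3%. The plan's figure is reproduced.
- Dropout: 69/0.95 = 72.6, so 73 per arm and 146 in total.
- Evaluable at 6 months: 2 × 69 = 138.

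The documents give no sample-size reasoning for the predictor aim, so 138 is the number used below.

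**2. Candidates.** SAP 9.5.1 names seven items: age, number of UUI episodes, functional bladder capacity, stress bother, irritative bother, type of MUI and anterior prolapse. Type of MUI has three levels, which makes about 8 degrees of freedom. The diary item is given only as an example, so the list is open. I used 8, 12 and 15 candidates, and stay criteria of 0.05 and 0.10. All of these beyond the named 8 are assumptions.

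**3. Backward selection on pure noise.** For k independent candidates, the chance that at least one passes level a is 1 − (1 − a)^k. The simulations used n = 138; those for 8 and 15 candidates forced in eight sites, age group and treatment, and set the correlation between candidates at 0 or 0.3.

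| Candidates | Stay criterion | Formula | Simulated |
|---|---|---|---|
| 8 | 0.05 | 34% | 34–35% |
| 8 | 0.10 | 57% | 58–59% |
| 12 | 0.10 | 72% | 70–71% |
| 15 | 0.05 | 54% | 56% |
| 15 | 0.10 | 79% | 79–81% |

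With 8 to 15 candidates, the selected noise showed an apparent partial R-squared of about 0.05 to 0.07. In new women the corresponding figure was about −0.05 to −0.08.

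**4. Threshold search on pure noise.** With n = 138 and an assumed 70% success rate, the best cut-point had a mean apparent Youden index (sensitivity + specificity − 1) of 0.16 for 1 measure, 0.24 for the best of 10 and 0.26 for the best of 20. The true value is 0. With 10 to 20 measures correlated at 0.5 it was still 0.23 to 0.25.

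In a separate run with assumed failure rates of 10% to 50%, a single noise measure gave a best cut at nominal p<0.05 in 41% to 44% of trials. The apparent gap in success rate was then 12 to 20 percentage points. For 10 to 26 independent measures the gap was 19 to 33 points. The true gap is 0.

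**5. Does resampling the whole search help?** With 26 noise measures and n = 138, measure and cut-point were searched again inside each fold of 10-fold cross-validation.

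| Assumed failure rate | Gap, same women | Gap, cross-validated | Gap, new women |
|---|---|---|---|
| 10% | 22 points | 0.8 | 0 |
| 20% | 28 points | 0.3 | 0 |
| 30% | 31 points | 0.3 | 0 |

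**6. Prognosis or choice of treatment?** SAP 9.5.1 lists treatment group only among the adjustment factors, and no treatment-by-predictor interaction is specified. If one were added, the standard error of the treatment difference is 46.5 × √(2/69) = 7.92 points. For a predictor that splits women in half, the interaction has standard error 2 × 7.92 = 15.8. The detectable interaction is (1.96 + 0.84) × 15.8 = 44 points at 80% power, or (1.96 + 1.28) × 15.8 = 51 points at 90%, against an MID of 26.

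**The case against.** The strongest reply is that SAP 9.5.1 is not the final plan for this aim. It recaps the protocol and says a separate SAP will document the methods before the analysis begins, and SAP 2 agrees. A reader might infer that performance will be judged on the women used to build the models. The documents do not show that: they are silent on validation, and the plan that would settle it is not available. This stands, and it makes the point conditional. It does not remove the point, because SAP 9.5.1 already commits to backward selection and the threshold search, and nothing requires the separate plan to be fixed before unmasking.

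Second, the aim is exploratory and its p-values are descriptive. That is true and should be kept in view, but a descriptive label does not correct an inflated R-squared or a searched cut-point.

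Third, most of the simulation inputs are assumed, and the setting closest to the text (8 candidates, p<0.05) gives about 35% rather than 80%. Hence the range. The retained noise also explains little variance, and a Youden index of 0.26 is modest; few readers would mistake either for a strong rule.

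Fourth, a reader might infer from Protocol 2.9 and 2.10 that the output would be rules for choosing between Botox A and sling. With no treatment-by-predictor interaction in the plan, the models as written identify prognostic factors only.

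**Conclusion.** The concern holds in conditional form. The plan commits to selection and threshold search in about 138 women without naming internal validation. If the separate SAP adds none, reported performance would be optimistic by roughly the amounts shown: noise retained in about 35% to 80% of trials, and an apparent Youden index of 0.16 to 0.26 where the truth is 0. These figures rest on an assumed 70% success rate, 8 to 15 candidates, stay criteria of 0.05 or 0.10, and 1 to 20 searched measures. They describe the extreme case in which no predictor carries information. This is a cheap improvement to an exploratory aim, not a defect in the trial's main comparison.

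**What to change.** Add to SAP 9.5.1, and carry into the separate predictor SAP:

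- All predictor selection, cut-point search and machine-learning tuning are repeated inside bootstrap samples or repeated cross-validation.
- Optimism-corrected R-squared, AUC, sensitivity and specificity are the headline figures, with the selection frequency of each predictor.
- Results are described as prognostic and hypothesis-generating, because no treatment-by-predictor interaction is specified.

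The cost is extra programming for a secondary manuscript and no new data. The downside is that the reported accuracy will look less favourable.

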9.5.2 Cost-effectiveness analysis

The EQ-5D and the SF-6D will be used to calculate QALYs. Methods for cost-effectiveness analysis from the protocol are included here and will be expanded upon is a cost-effectiveness analysis SAP that will be developed prior to analysis of the cost effectiveness data, which will be reported in a secondary manuscript.

Differential mean costs and differential mean QALYs between the two treatment groups will be estimated using multiple regression analysis. Specifically, a generalized linear model with appropriate link function (e.g., log-link) and response probability distribution (e.g., gamma distribution) will be used to analyze costs due to the potential skewness and heteroscedasticity of medical expenditure data, while an ordinary least squares regression will be used for analyzing QALY data. The models will account for stratification factors of study site and age group, as well as other characteristics of the subjects that are found to differ significantly between the groups. When estimating QALYs, we will also adjust for subjects' baseline utility scores to account for potential imbalance in baseline utility between the two treatment groups.

We will calculate the incremental cost-effectiveness ratio (ICER), which is the differential mean costs divided by the differential mean QALYs between the two groups, to assess the additional costs associated with each additional QALY gained. Our base case analysis will be conducted based on subjects with complete data. Sensitivity analysis will be conducted to include subjects with incomplete data using the multiple imputation method. Non-parametric bootstrapping resampling technique will be used to derive the 95% confidence interval for the ICER. In addition, cost-effectiveness acceptability curve (CEAC) will be generated to illustrate the likelihood that one treatment is more cost-effective than the other with various ceiling cost-effectiveness ratios.

We plan to conduct supplemental analyses using alternative outcome measures, such as incremental cost per reduction in UIE/day.

The cost-effectiveness evaluations will be conducted as within-trial comparisons. A decision analytic model will also be developed from trial data to evaluate the trajectory of the cost-effectiveness ratio.

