women with MUI could potentially worsen co-existing UUI. In ESTEEM, within the sling only group, UDI-total, UDI-irritative, and UDI-stress scores at 12 months improved and exceeded the corresponding MIDs of 35 points (SD 50.4), 15 points (SD 25.6) and 8 points (SD 21.5) respectively.¹⁰ These findings suggest that the mid-urethral sling alone is a highly effective treatment for stress component of MUI and can actually improve the UUI component. However, it remains unknown the extent to which women with MUI would require additional treatment for SUI if the more bothersome UUI symptoms were treated first.

3. **Predictors of treatment.** The ESTEEM trial showed that women with worse baseline OAB symptoms are more likely to be treatment failures at 12 months. Specifically, DO on urodynamics and previous OAB medication use were predictors of treatment failure in both groups. In addition, there was an interaction between baseline UDI-irritative score and treatment type with respect to predicting treatment failure. Women with higher baseline UDI Irritative scores randomized to sling only had higher odds of failure, compared to combined treatment. For each 10 point increase in UDI-irritative score, the adjusted odds of failure increased by 1.45 in the sling only group. This effect was not seen in the combined group.

The MUSA trial builds on the findings of ESTEEM but has several important differences from ESTEEM.

1. **The primary hypothesis of MUSA is different from ESTEEM.** The ESTEEM trial primarily treated the stress component of SUI using the mid-urethral sling and determined if behavioral treatment provided additional benefits. MUSA will determine if for women with MUI, an office-based treatment directed at the more bothersome urgency component, Botox A, is more effective than a surgical treatment directed at the stress component, mid-urethral sling.

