7.2 Adjustments for Covariates

Indicator variables for the study stratification factors of site and age group ($\geq 65, < 65$) will be included as covariates in most efficacy analyses performed for this study (details in section 9). The baseline value of the outcome variable will also be a covariate in models of change from baseline.

Additionally, demographic and baseline characteristics will be compared between study arms using a t-test for continuous measures, Mantel-Haenszel mean score test using standardized midrank scores for ordinal measures, and Cochran Mantel-Haenszel chi-square tests for general association for categorical measures. If these analyses suggest that a substantial difference exists among arms for an important characteristic, supportive exploratory analyses of the primary efficacy outcome adjusting for the characteristic may be explored.

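### The cost and QALY models take their extra covariates from significance tests of baseline differences between randomised arms, so chance sets the adjustment behind the ICER

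*SAP*

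**What the plan says.** SAP 9.5.2 fixes site and age group as covariates in both the cost and the QALY regressions and adds baseline utility to the QALY regression without any test. Both models then also adjust for further variables: "as well as other characteristics of the subjects that are found to differ significantly between the groups". No candidate list and no significance level are given. Protocol 6.2.3 (exploratory aim 5) has the same rule for 6 months, and the addendum in Protocol Section 10 repeats it for 12 months. SAP Section 2 and 9.5.2 announce a separate cost-effectiveness SAP that will build on these methods.

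SAP 7.2 has a looser relative of the rule. Baseline characteristics are tested between arms, and a supportive exploratory analysis of the primary outcome may follow: "If these analyses suggest that a substantial difference exists among arms for an important characteristic". Neither the size of difference nor the importance of the characteristic is defined.

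Two other places bear on this. SAP 7.8 classes baseline p-values as descriptive. Protocol 2.1.1, reporting on the ESTEEM trial, says that "DO on urodynamics and previous OAB medication use were predictors of treatment failure in both groups".

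**The concern.** With concealed randomisation, every baseline difference between arms is a chance finding, whether or not it is significant. A test of that difference carries no information on whether the variable predicts cost or QALYs, which is what makes adjustment worthwhile. The rule can therefore admit a variable with no prognostic value and omit a strong predictor that happens to be balanced.

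Three consequences follow for the ICER:

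- The covariate set cannot be known until the arms have been compared, and another randomisation would give another set.
- The cost model may contain no measure of baseline severity or utility, although UDI, bladder diary and utility instruments are all collected at baseline.
- The SAP does not say whether covariate selection is repeated within each bootstrap resample. If it is not, the interval for the ICER ignores the selection step.

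The rule also conflicts with the plan itself: SAP 7.8 calls baseline p-values descriptive, while 9.5.2 uses significance to build a model. The unconditional adjustment for baseline utility, in the same section, already follows the better principle.

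**Working it through.** **1. Sample size, to fix n for the check.** Inputs from SAP Section 6 and 7.8: "alpha was set at 0.05 and power was set at 90" per cent; "The primary hypothesis will be tested at a nominal two-sided type I error of 0.05"; "The MID for ESTEEM UDI-Total is 26, and the SD=46.5 from the analysis model, resulting in an effect size = 0.56"; "MUSA will randomize 146 women to treatment with Botox or Sling in a 1:1 ratio"; "we plan for 5% discontinuation rate by 6 months".

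Normal approximation: n = 2 × (1.960 + 1.282)² × (46.5/26)² = 67.2, so 68 per arm. The noncentral t calculation gives 69. Then 69/0.95 = 72.6, so 73 per arm and 146 in total. The plan's figures reproduce. None of them depends on the covariate rule.

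**2. How often chance alone flags something.** For k independent tests at 0.05, P(at least one significant) = 1 − 0.95^k. SAP 8.3 lists about 9 to 12 variables, depending on how race and ethnicity and the time-to-treatment items are counted.

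- k = 9: 37%
- k = 10: 40%
- k = 12: 46%
- k = 20: 64%

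These are indicative. The 0.05 level is assumed, 9.5.2 is not tied to the 8.3 list, and some items are correlated (parity with gravidity, age with menopausal status). The firmer statement concerns a single variable: at 0.05 it enters about 5% of the time, whatever its prognostic strength.

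**3. Cost in precision.** Take one covariate with correlation r to the outcome, a linear model and 69 per arm. In units of 2/n times the outcome variance:

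- Always adjusted: (1 − r²)(1 + 1/134). The second factor, about 1.0075, is the price of estimating one slope.
- Adjusted only if the baseline test gives p < 0.05: about (1 − r²)(1.0021) + 0.72 r². Here 0.72 = 0.95 − 2 × 1.96 × 0.0584, the share of the chance-imbalance variance left in the estimate when the test is not significant. The slope term shrinks to 0.28/134 = 0.0021.

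| Assumed r | Test-selected | Always adjusted | Variance ratio |
|---|---|---|---|
| 0.2 | 0.991 | 0.967 | 1.02 |
| 0.3 | 0.977 | 0.917 | 1.07 |
| 0.4 | 0.957 | 0.846 | 1.13 |
| 0.5 | 0.932 | 0.756 | 1.23 |

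At r = 0.1 the penalty is about 0.2%. Simulations agree: 6 to 7% at r = 0.3, 12 to 14% at 0.4, and about 23% at 0.5.

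**4. Error rates.** These come from a simulation of 40,000 trials with 69 per arm. Under no effect, the test-selected rule has type I error 0.047, 0.042 and 0.036 at r = 0.3, 0.5 and 0.7, against 0.048 to 0.049 when the covariate is pre-specified. For a true effect of 0.5 SD, power is 0.84 against 0.86, 0.84 against 0.92, and 0.85 against 0.98. The rule is mildly conservative and wasteful; it does not inflate type I error.

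**The case against.** The strongest reply is that little rests on this rule, and much of that reply stands.

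- **Primary analysis.** A reader might infer that the primary result depends on baseline testing. It does not: SAP 9.3 fixes baseline UDI, site and age group. SAP 7.2 offers only an optional exploratory addition, and its trigger is a substantial difference on an important characteristic, not significance alone.
- **Known predictors.** A reader might infer that known predictors are ignored. Age group, which Protocol 3.3 calls a well-known predictor, is in every model. The UDI-irritative score is part of the UDI-total, whose baseline value is in the primary model. Baseline utility is in the QALY model.
- **Relevance of the ESTEEM predictors.** They concern treatment failure in a sling trial, not costs or QALYs. Protocol 3.3 suggests that UUI severity may act in opposite directions in the two arms, in which case one common term gains less.
- **Size.** A single headline, such as a loss of about 16 of 138 evaluable women (138 × (1 − 1/1.13)), holds only at r = 0.4, which no document supports. After adjustment for baseline UDI, site and age group, the remaining correlation in a supportive primary model may well be lower.
- **Status.** Cost-effectiveness is an exploratory aim whose p-values are not judged for significance, and its own SAP is still to come.

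The last point does not remove the concern. The pending SAP is described as expanding on the methods given here, so the rule carries forward unless it is deleted.

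**Conclusion.** The point holds for the cost and QALY models. Beyond the fixed terms, their covariates are chosen by a criterion that chance governs under randomisation, and the cost model has no guaranteed severity or utility term. In SAP 7.2 the weakness is milder: undefined terms, and baseline tests used to prompt an optional analysis.

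The effect is lost precision and avoidable analyst discretion in exploratory analyses. The documents do not support a claim of a biased or inflated primary result, or of too small a trial. The variance penalty runs from about 2% to 23% for correlations from 0.2 to 0.5. This assumes one covariate, a linear model, 69 per arm and selection at 0.05. The gamma or log-link cost model was not simulated, so the figures are a guide for costs and closer to the case for the least-squares QALY model.

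**What to change.** - **Cost and QALY models.** Delete the significance rule in SAP 9.5.2, Protocol 6.2.3 and the addendum, and do not carry it into the cost-effectiveness SAP. Name the covariates there before the arms are compared. A workable list for both models is site, age group, baseline utility, baseline UDI-total and baseline UUI episodes per day.
- **Supportive primary model (SAP 7.2).** Name its covariates in advance, for example prior OAB medication and detrusor overactivity on top of the planned terms. Drop baseline tests as the trigger.
- **Missing baseline values.** State how they are handled. The base-case cost-effectiveness analysis uses women with complete data, so each added covariate could remove some.
- **Optional.** Leave p-values out of the baseline table.

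The cost is a wording change, a few degrees of freedom and the missing-value rule. The variables are already collected and the sample size stays at 146.
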